9.1.2 Adverse events analyses

All adverse events (AEs) recorded on the adverse events CRF will be coded using the current Medical Dictionary for Regulatory Activities (MedDRA). Note that adverse events that started or were ongoing during any gap between the completion of the prior study and enrollment into this CFTY720D2399 study, even if the adverse event was not ongoing at the time of CFTY720D2399 enrollment, can be recorded on the CFTY720D2399 adverse events CRF.

In AE summaries, primary system organ classes will be displayed in alphabetical order and preferred terms (within each system organ class) will be sorted by descending frequency in the fingolimod any dose column.

There are two categories of AE summaries in this study which are presented in the sections below.

9.1.2.1 Adverse events during long-term follow-up study part I

Adverse events reported during the long-term follow-up study part I will be summarized for the safety set. Unless otherwise specified, all non-serious adverse events recorded in the CFTY720D2399 database with onset on or after first dose date of fingolimod among all studies to last dose date of fingolimod + 45 days are included. All serious adverse events

(SAEs) recorded in the CFTY720D2399 database with onset on or after the first dose date of fingolimod among all studies are also included in the summaries.

Adverse events reported during the long-term follow-up study part I will be summarized by primary system organ class (SOC) and preferred term (PT), and will show the number and percentage of patients with at least one adverse event in each SOC or PT category. Similarly, adverse events by study drug relationship (AEs suspected to be study drug related, AEs not suspected to be study drug related, and AEs regardless of study drug relationship), SAEs, SAEs by study drug relationship, suspected study drug related AEs, and AEs leading to study drug discontinuation will also be summarized by SOC and PT.

AEs and SAEs which are not considered to be known effects of fingolimod treatment (i.e., excluding those listed in the most recent version of Core Data Sheet), will be summarized by PT only.

To determine which AEs occur after discontinuation of fingolimod treatment, all AEs reported with onset date after the last dose of fingolimod until the end of the long-term follow-up study part I will be summarized by SOC and PT for the follow-up set.

Principal cause of death during the long-term follow-up study part I will be summarized by SOC and PT. All deaths recorded in the CFTY720D2399 database with onset on or after the first dose date of fingolimod (among all studies) will be included in the summary.

All information pertaining to any AE with severity information, SAEs, AEs leading to study drug discontinuation, deaths and neoplasms system organ class events that reported during the long-term follow-up study part I will be listed for the safety set. Additionally, adverse events, SAEs and all deaths recorded during the long-term follow-up study part I will be listed for the subgroup of patients from studies D2312 and D2402 in the enrolled set.

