**Data analysis:**

Unless otherwise specified, the following pertains to the entire study (Study Parts One and Two).

Long-term safety will be assessed based on adverse events (AEs), laboratory and vital signs as well as other investigations performed when clinically indicated. Analysis of the safety variables will be conducted on the safety set.

Incident rates (IRs) of adverse events per 100 patient-years will be summarized by highest assigned fingolimod dose (fingolimod 0.5 mg/day and any dose of fingolimod).

To further evaluate the risk with longer fingolimod exposure duration, IR if adverse events reported with different fingolimod exposure durations will be compared.

In addition, the incidence of adverse events (new or worsened from the long-term extension baseline) reported during the long-term extension will be summarized by primary system organ class and preferred term as frequency count and percentage of patients with adverse events.

The incidence of death, serious adverse events (SAEs), AEs leading to discontinuation, and other significant AEs will be summarized separately by primary system organ class and preferred term.

Laboratory data will be summarized using summary statistics of raw data and change from baseline values. For liver function tests, the frequencies and percentages of patients with elevations of 1, 2, 3, 5, and 10 times upper limit of normal will be summarized by visit (Study Part One only).

Vital sign data will be summarized as descriptive statistics for change from baseline value. The incidence rates of notable vital sign abnormalities will be summarized.

Summary statistics for ECG parameters (including pre-dose ECG for patients who have this evaluation done) will be summarized by visit. Incidence of abnormal ECGs by type of abnormality will be presented.

The incidence of macular edema events will be summarized as frequency distributions. The patient data listing will also be provided.

Pulmonary function test data (FEV1, FVC, and DLCO, percentage of predicted value for these three variables, and smoking status) will be summarized.

The skin assessment will be summarized based on abnormal findings.

The safety data will also be summarized by subgroups for the supportive safety analysis purpose.

The safety data obtained after discontinuation of the study drug will be summarized.

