## 7 Safety monitoring

### 7.1 Adverse events

An adverse event is the appearance or worsening of any undesirable sign, symptom, or medical condition occurring after starting the study drug even if the event is not considered to be related to study drug. Study drug refers to the investigational drug, fingolimod given during this study. Medical conditions/diseases present before starting study drug are only considered adverse events if they worsen after starting study drug. Abnormal laboratory values or test results constitute adverse events only if they induce clinical signs or symptoms, are considered clinically significant, or require therapy.

The occurrence of adverse events should be sought by non-directive questioning of the patient at each visit during the study. Adverse events also may be detected when they are volunteered by the patient during or between visits or through physical examination, laboratory test, or other assessments. All adverse events must be recorded on the Adverse Event eCRF pages with the following information:

1. the severity grade (mild, moderate, severe)
2. its relationship to the study drug(s) (suspected/not suspected)
3. its duration (start and end dates or if continuing at final exam)
4. whether it constitutes a serious adverse event (SAE)

An SAE is defined as an event which fulfills one or several of the following criteria:

- is fatal or life-threatening
- results in persistent or significant disability/incapacity
- constitutes a congenital anomaly/birth defect
- requires inpatient hospitalization or prolongation of existing hospitalization, unless hospitalization is for:
  - routine treatment or monitoring of the studied indication, not associated with any deterioration in condition (e.g. hospitalization for relapse treatment)
  - elective or pre-planned treatment for a pre-existing condition that is unrelated to the indication under study and has not worsened since the start of study drug
  - treatment on an emergency outpatient basis for an event not fulfilling any of the definitions of a SAE given above and not resulting in hospital admission
  - social reasons and respite care in the absence of any deterioration in the patient's general condition
- is medically significant, i.e., defined as an event that jeopardizes the patient or may require medical or surgical intervention to prevent one of the outcomes listed above

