#### **9.4.1.1 Adverse events (AEs)**

Incidence rates (IRs) of adverse events per 100 patient-years will be summarized by highest assigned fingolimod dose (fingolimod 0.5 mg/day and any dose of fingolimod) based on the fingolimod safety set.

To further evaluate the risk with longer fingolimod exposure duration, adverse events reported with different fingolimod exposure durations will be assessed based on the fingolimod safety set.

In addition, the incidence of adverse events (new or worsened from the long-term extension baseline) reported during the long-term follow up study will be summarized by primary system organ class and preferred term as frequency count and percentage of patients with adverse events based on the safety set.

- Any adverse events
- Serious adverse events (SAEs)
- Suspected study drug related adverse events
- Adverse events leading to discontinuation
- Deaths

All information pertaining to serious adverse events and deaths noted during this study will be listed by center and patient number.

The same analysis including data collected during the Study Part Two will be conducted for the subgroup of patients who entered Study Part Two.

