2.5 Analysis sets

The following analysis sets will be defined.

- **Enrolled set:** The enrolled set will include all patients who entered the long-term follow-up study part I (excludes long-term follow-up study screen failures), but will exclude patients with protocol deviation severity code of 8 (8=exclude from all analyses) in the long-term follow-up study part I.
- **Safety set:** The safety set will include all patients who entered the long-term follow-up study part I and received at least one dose of fingolimod in any study, but will exclude patients with protocol deviation severity codes of 5 (5=exclude from all safety analyses) and 8 (8=exclude from all analyses) in the long-term follow-up study part I. Note that all data reported in the long-term follow-up study part I will be analyzed, including assessments or events which started before the long-term follow-up study part I.
- **Fingolimod safety set:** The fingolimod safety set will include all patients who entered the long-term follow-up study part I and received at least one dose of fingolimod in any study, but will exclude patients with protocol deviation severity codes of 5 (5=exclude from all safety analyses) and 8 (8=exclude from all analyses) during the core study prior to entry to the long-term follow-up study part I. For patients with such protocol deviations after the core study, record level data associated with the protocol deviations will be excluded from the analysis.

- **Fingolimod full analysis set:** The fingolimod full analysis set will include all patients who entered the long-term follow-up study part I and received at least one dose of fingolimod in any study but will exclude patients with protocol deviation severity codes of 0 (0=exclude from all efficacy analyses) and 8 (8=exclude from all analyses) during the core study prior to entry to the long-term follow-up study part I. For patients with such protocol deviations after the core study, record level data associated with the protocol deviations will be excluded from the analysis.
- **Follow-up set:** The follow-up set will consist of all patients in the safety set who have any follow-up visit data or at least one safety record after the study drug discontinuation. It will be used for summary of adverse events and concomitant medications with occurrences after last dose of fingolimod only.

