9.1.2.2 Adverse events during the fingolimod treatment period

Unless otherwise specified, all non-serious adverse events with onset on or after first dose date of fingolimod among all studies to last dose date of fingolimod + 45 days are included. All serious adverse events (SAEs) with onset on or after the first dose date of fingolimod among all studies are also included in the summaries. Also, unless otherwise specified, adverse events will be summarized for the fingolimod safety set, by primary system organ class and preferred term, and will show the number of patients with at least one adverse event and the incidence rate of adverse events per 100 patient-years in each SOC or PT category.

The AE incidence rate (IR) is calculated per 100 patient-years. IR is defined as: the number of patients experiencing at least one event in a particular category, over the total patient-years of the “at risk” population for that event multiplied by 100. An underlying Poisson process for incidence rate within treatment group is assumed.

To calculate the total patient-years (time at risk) of the “at risk” population:

1. For patients who have a particular AE category, sum the number of days from first dose date of fingolimod among all studies to the first occurrence of that particular AE category

2. For patients who did not have a particular AE category, sum the number of days from first dose date of fingolimod among all studies to last dose date of fingolimod + 45 days.
3. Add the time at risk for patients who had a particular AE category with the time at risk for patients who did NOT have a particular AE category. This is the total time at risk of that AE category.
4. Divide the total time at risk by 365.25.

Incidence rate of adverse events will be presented for the fingolimod safety set and for the subgroup of fingolimod safety set patients from phase II/III studies, by SOC and PT. Incidence rate of AEs, excluding AE listed in the core data sheet, will be presented by PT. Incidence rate of AEs that fulfill the risk search term (defined in the case retrieval sheet) will be presented by risk name and lower level terms. Similarly, all above indicated AE IR summaries will be conducted for SAEs.

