To further evaluate the long-term AE rate (based on patient count and percentage) within a particular fingolimod treatment duration, an analysis based on yearly intervals since first dose of fingolimod will be conducted. For summaries on this set of patients, all AEs and SAEs with onset on or after first dose date of fingolimod (among all studies) to last dose date of fingolimod are included. Each yearly interval will contain 360 days. For example: Year 1 will consist of Day 1 to Day 360, Year 2 will consist of Day 361 to Day 720, Year 3 will consist of Day 721 to Day 1080, Year 4 will consist of Day 1081 to Day 1440, Year 5 will consist of Day 1441 to Day 1800, and so on. Patients will be summarized within a particular yearly interval if they have been receiving study treatment for at least one day in that particular interval. The number and percentage of these patients who have adverse events with onset date occurring during the interval will be summarized. For example, for the Year 1 group, patients with at least one day exposure to fingolimod will be included, and AEs with onset date occurring between Day 1 and Day 360 will be summarized. For the Year 2 group, patients with at least 361 days exposure to fingolimod will be included, and AEs with onset date occurring between Day 361 and Day 720 will be summarized. The same will be done for other intervals.

Adverse events summarized by year will include the following:

- Adverse events, by yearly interval, primary system organ class, and preferred term
- Serious adverse events, by yearly interval, primary system organ class, and preferred term
- Adverse events that fulfill the risk search term, by yearly interval
- Serious adverse events that fulfill the risk search term, by yearly interval

Intervals will be included based on the length of fingolimod exposure. Risk search terms are defined in Novartis' case retrieval sheet. Associated summaries will be presented by risk name and lower level terms.

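### SAP Part I starts its follow-up-study n (%) AE tables at the first fingolimod dose in any study; the protocol asks for AEs new or worsened since D2399 baseline, and no Part I table shows those alone

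*SAP*

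**What the plan says.** **Protocol.** Section 9.4.1.1 defines the n (%) tables by system organ class and preferred term, on the safety set, as covering AEs "new or worsened from the long-term extension baseline) reported during the long-term follow up study". The synopsis repeats the condition: "new or worsened from the long-term extension baseline) reported during the long-term extension will be summarized". Section 9.4.1 reserves the safety set for analyses of follow-up-study data only. Section 7.1, where study drug means the fingolimod given in this study, points the same way: "Medical conditions/diseases present before starting study drug are only considered adverse events if they worsen after starting study drug".

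**SAP Part I.** Section 9.1.2.1 covers AEs during Part I on the safety set. It includes "all non-serious adverse events recorded in the CFTY720D2399 database with onset on or after first dose date of fingolimod among all studies", ending 45 days after the last dose. SAEs have the same start and no end date. Neither rule requires the event to be new or worsened.

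Two other passages show that earlier events are expected. The safety-set note in section 2.5 says that all data reported in Part I are analysed, "including assessments or events which started before the long-term follow-up study part I". Section 9.1.2 says that AEs from the gap between the prior study and this one, "even if the adverse event was not ongoing at the time of CFTY720D2399 enrollment, can be recorded on the CFTY720D2399 adverse events CRF".

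**The concern.** These tables answer the primary objective, long-term safety and tolerability. The protocol gives them a baseline: the patient's state on entering D2399. The SAP replaces it with the first fingolimod dose, which for many patients was taken years earlier in another trial. An AE that began in that interval, was recorded again in D2399 and did not worsen is then presented as an event during Part I. The clearest case is an event that started and ended between studies. A reader of the Part I tables could not tell how much of a percentage reflects events arising in D2399. This matters most for rare terms, where a few records change the picture, and Protocol 1.1 says that long-term data are needed to estimate rare or time-dependent events better.

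**Working it through.** No planned figure depends on this rule, so there is none to reproduce. The check compares the two rules and then looks for any other Part I table that fills the gap.

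**1. The rules applied to each kind of D2399 record** (patient already treated with fingolimod before D2399)

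| Record | Protocol 9.4.1.1 | SAP Part I 9.1.2.1 |
|---|---|---|
| Onset after D2399 baseline, no later than 45 days after last dose | counted | counted |
| Onset between first fingolimod dose and D2399, worsened in D2399 | counted | counted |
| Same early onset, not worsened, recorded again | not counted | counted |
| Gap AE resolved before enrollment | not counted | counted |
| Non-serious AE, onset more than 45 days after last dose | counted | not in the main tables |
| SAE, onset more than 45 days after last dose | counted | counted |

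The fifth row can occur: Protocol Table 6-1 collects AEs at follow-up visits 3 and 6 months after the last dose. In the SAP these late events appear only in the separate follow-up-set table.

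**2. Direction.** For a given term, with the first two rows treated alike, the SAP count minus the protocol count equals the patients counted only through rows 3 or 4, minus the patients who would be counted only through row 5. Neither quantity is in the documents, so the sign is not fixed.

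**3. Who is affected.** Only AEs recorded in the D2399 database enter these tables; AE histories from earlier studies are not pooled in. If the first fingolimod dose was given in D2399, the two start dates coincide and the earlier start changes nothing.

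**4. Other Part I summaries.** None isolates all onsets from D2399 entry:
- The incidence rates in section 9.1.2.2 use time at risk from the first-ever dose: "sum the number of days from first dose date of fingolimod among all studies to the first occurrence".
- The yearly tables have the same origin: "an analysis based on yearly intervals since first dose of fingolimod will be conducted".
- The follow-up-set table covers only onsets after the last dose.

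**5. Scale.** Take 4,150 patients (Protocol, Amendment 11 rationale) as the denominator. The safety set may be smaller, which would make each patient weigh more.
- One patient: 1 / 4,150 = 0.000241, or 0.024 percentage points.
- 0.1 point: 0.001 × 4,150 = 4.15, about 4 patients.
- 1 point: 0.01 × 4,150 = 41.5, about 42 patients.

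This shows sensitivity. It does not estimate how many such patients there are.

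**The case against.** The strongest defence is that data capture already applies most of the protocol's filter. Under section 7.1 an earlier condition becomes an AE in this study only if it worsens, so few unworsened events should be in the database. The safety-set note could refer to worsened AEs that keep their original onset date, and those belong in the tables. This limits the number affected and stands to that extent. It does not remove the gap AEs, which SAP section 9.1.2 allows onto the D2399 form even when they were over before enrollment.

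A second defence is the general rule in Protocol section 9 that data are analysed from the first fingolimod dose. That rule yields where something else is mentioned, and section 9.4.1.1 names another baseline for these tables.

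Third, the analysis is descriptive, the SAP discloses that earlier-starting events are included, and all AEs are listed, with dates as held in the database. A determined reader could find early onsets. That lowers the stakes, but rebuilding percentages by preferred term from listings is not practical.

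Fourth, filtering the main tables on onset date could move them further from the protocol, because worsened AEs with an earlier onset would drop out. This stands, and the fix therefore adds tables and leaves the existing ones in place.

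A reader might also infer that the SAP percentages can only be too high. The documents do not support that, because the 45-day limit works in the opposite direction.

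**Conclusion.** The SAP departs from an explicit protocol rule for primary-objective safety tables, and nothing in Part I supplies the missing view. It should be fixed, but it does not show that any reported percentage will be materially wrong. The size is unknown, may be zero, and may go either way. The conclusion rests on reading the long-term extension baseline as entry to D2399, and on some gap or carried-over AEs being recorded in D2399, which the SAP expects but does not quantify.

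A reader might infer that Part 2 has the same fault to the same degree. It does not. SAP Part 2 9.1.2.1 uses the same start, but AEs that began during Part One already meet the protocol's D2399-baseline rule. Section 9.1.2.1.1 adds tables of newly-occurring AEs and SAEs, and the incidence rates in 9.1.2.1.2 state their own window from the first Part 2 dose. What remains is mainly labelling. Nor do the documents show that anchoring the newly-occurring tables on the Part 2 consent date is unworkable: Table 6-2 footnote 3 makes the consent item not applicable to patients coming from Part One, while Amendment 10 required a revised consent. Whether the date is stored cannot be settled from the text.

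**What to change.** 1. Add to SAP Part I tables of n (%) by system organ class and preferred term for AEs and SAEs, with drug-related versions. Count AEs with onset on or after the first D2399 dose, plus earlier AEs recorded as worsened after that dose where the data allow. State that these tables answer Protocol 9.4.1.1.
2. Keep the existing wide-window tables, including those for discontinuation and death, and label them as including AEs that began before D2399.
3. In SAP Part 2, only label the main n (%) tables as including AEs that began before Part 2.

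The cost is a few extra tables, some wording and a date condition. SAP Part I section 2.3.2 already derives study day from the first D2399 dose. The weak spot is the worsened component: Protocol 7.1 lists one severity grade per AE and asks for changes to be assessed at each visit, but does not say that dated changes are stored. If they are not, a footnote should say that this component is incomplete.
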